4.0 SUBJECT SELECTION

4.1 Subject Identification and Recruitment

4.1.1 Research Match

ResearchMatch.org is a national electronic, web-based recruitment tool that was created through the Clinical & Translational Science Awards Consortium in 2009 and is maintained at Vanderbilt University Medical Center. There is no cost for researchers at participating institutions in the ResearchMatch Network to use ResearchMatch for the purposes of conducting recruitment feasibility analysis or participant recruitment. The Vanderbilt University Medical Center IRB provides oversight for ResearchMatch as a recruitment tool). However, individual requests to use ResearchMatch as a recruitment tool are required to be approved by the participating institution's IRB. OhioHealth is an approved ResearchMatch institution.

ResearchMatch[©] consists of a registry of volunteers that have signed up to receive notifications about potential research studies. ResearchMatch[©] provides standard notification language that will be received by all ResearchMatch[©] volunteers who may be eligible for a given study. When a volunteer is sent a notification about a study, they will reply ("yes" or "no") using the appropriate notification quick links. When volunteers select "yes" to affirm their interest in participating, ResearchMatch[©] will release their contact information through the online portal to the Principal Investigator (PI) or research team. All information will be managed per strict ResearchMatch[©] Guidelines. Research staff will then call volunteers to prescreen for medical history pertaining to the study and determine eligibility. If the volunteer is interested, the consent will be sent via email for review, and the Baseline visit will be scheduled at the OhioHealth Research Institute.

4.1.2 Identification and Recruitment

Group 1: Healthy volunteers will be identified from the community using recruitment flyers posted at OhioHealth hospital campuses (App. B) and notifications in ResearchMatch[©] (App. C). ResearchMatch[©] notifications will be limited to registry participants located within a 25 mile radius of OhioHealth Riverside Methodist Hospital. OhioHealth associates can be included in the healthy volunteer cohort.

Group 2: Patients presenting to the OhioHealth Riverside Methodist Hospital Critical Limb Care Center with a diabetic lower extremity ulceration and/or arterial insufficiency lower extremity ulceration will be pre-screened for possible inclusion in the study. If determined preliminarily eligible, a research staff member will either approach the patient at their visit to the Critical Limb Care Center, or contact them by phone following their visit, if necessary.

4.2 Informed Consent

Written informed consent using the most current Institutional Review Board (IRB)-approved informed consent form (ICF) will be obtained from all subjects prior to any study-specific tests or procedures performed (App. D & E). This does not include those procedures or tests that are obtained in the normal course of the subject's routine care.

IRB# 1331496 Page 20 Version 6.0

4.3 Enrollment

Subjects will be considered enrolled once signed informed consent has been obtained. Subjects that do not present for the initial Noxsano Bandage application appointment will be withdrawn from the study and replaced.

All subjects who have been consented will be registered in the Research Electronic Data Capture (REDCapTM) database and will be assigned a unique subject study number.

The screening and enrollment log will also be completed to document the outcome of all subjects who underwent screening (App. F). The screening and enrollment log will contain the enrollment and study number of subjects who were enrolled, or the reason for non-enrollment of subjects who did not meet inclusion/exclusion criteria.

Group 1 and Group 2 subjects will be screened according to the protocol inclusion and exclusion criteria. Each of the criteria in sections 4.4 and 4.5 must be met in order for a subject to be considered eligible for this study.

4.4 Inclusion Criteria

Group 1: Subjects must meet **all** of the following criteria to be eligible for enrollment:

- 1. Subject is \geq 18 and \leq 80 years of age.
- 2. Subject is white, black or African American
- 3. Subject has provided written informed consent.
- 4. Subject is willing to comply with study follow-up requirements.
- 5. Subject has intact skin on lower extremities.

Group 2: Subjects must meet **all** of the following criteria to be eligible for enrollment:

- 1. Subject is \geq 18 and \leq 80 years of age.
- 2. The wound to be treated with the Noxsano bandage has a baseline wound surface area of < 25 cm².
- 3. Subject has provided written informed consent.
- 4. Subject is willing to comply with study follow-up requirements.
- 5. Subject with at least **one** of the following:
 - a. Diabetic lower extremity ulceration with a hemoglobin A1c (HgbA1c) value ≤ 9.0, drawn within 3 months prior to study participation¹, and/or
 - b. Arterial insufficiency lower extremity ulceration with a post-revascularization ankle-brachial index (ABI) value of ≥ 0.40 and ≤ 0.80 on the involved extremity, performed within 3 months prior to study participation¹, and/or

IRB# 1331496 Page 21 Version 6.0

_

¹ Baseline measures of HgbA1c or ABI (within 3 months prior to consent) must be available for inclusion.

c. Diabetic and/or arterial insufficiency lower extremity ulceration deemed ineligible for revascularization with 3 months prior to study participation

4.5 Exclusion Criteria

Group 1: Subjects will be excluded from the trial if **any** of the following criteria are met:

- 1. Subject is < 18 or ≥ 80 years of age.
- 2. Subject has a history of diabetes, arterial insufficiency, or osteomyelitis.
- 3. Subject has a known hypersensitivity to adhesives.
- 4. Subject is on any prescription medications, including contraceptives. Due to the short duration of the procedure period (3 days), subjects who initiate prescription medications during study participation will continue in the study.
- 5. Subject is pregnant, plans to become pregnant during the study period, or is breastfeeding.
- 6. Subject is non-English speaking or reading.
- 7. Subject is unable to give informed consent.

[figure not shown]
Group 2: Subjects will be excluded from the trial if **any** of the following criteria are met:

- 1. Subject is < 18 or ≥ 80 years of age.
- 2. The wound to be treated with the Noxsano bandage has a baseline wound surface area of ≥ 25 cm².
- 3. The wound to be treated with the Noxsano bandage is a plantar wound.
- 4. Subject with diabetes with an HgbA1c value of > 9.0, drawn within 3 months prior to study participation².
- 5. Subject with arterial insufficiency with an ABI value of < 0.40 or > 0.80, performed within 3 months prior to study participation³.
- 6. The wound to be treated with the Noxsano bandage has osteomyelitis contiguous with the treatment site.
- 7. Subject with peripherally-inserted central catheter (PICC) line antibiotic treatment within the previous 6 months.

IRB# 1331496 Page 22 Version 6.0

² Hemoglobin A1c is known to be significantly associated with wound healing rates, making it an important marker in the prediction of wound healing in diabetic patients [29]. A cutoff of 9.0% was chosen to exclude those with uncontrolled diabetes at highest risk for poor healing outcomes, as well as surgical complications including wound infections [30].

³ Patients with a normal-to-borderline ABI (> 0.80) are not characterized or diagnosed as having arterial insufficiency and are not referred to a vascular specialist; on the opposite end of the spectrum, those with severe arterial disease (< 0.40) typically proceed directly to hyperbaric treatment.

- 8. Subject requiring any type of amputation on the treatment limb within 3 months prior to study participation.
- 9. Subject with a known hypersensitivity to adhesives.
- 10. Subject is on active steroid therapy (does not include inhaled steroids).
- 11. Subject is pregnant, plans to become pregnant during the study period, or is breastfeeding.
- 12. Subject is non-English speaking or reading.
- 13. Subject is unable to give informed consent.
- 14. Subject is currently enrolled in another interventional study.

IRB# 1331496 Page 23 Version 6.0

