- ♦ *Electrodes* Non-woven conductive carbon fiber cloth. The carbon fiber allows efficient reaction with the mediator and prevents galvanic corrosion of the electrode that would occur with a metal electrode.
- ♦ *Connectors* 3M non-metallic conductive tape.
- ♦ *Battery* Three volt (3V) lithium ion battery. The battery is similar to standard coin cell watch batteries such as the CR2032, but has a higher operating temperature allowing for steam sterilization.
- ♦ *Hydrogel formulation* Medical grade cross-linked poly-(acrylic acid), sodium nitrite, buffer (pH 7.5-8.0), and an electrochemical mediator. The formulation is 'activated' by soaking the dressing in sterile water. The final concentration of sodium nitrite in the wet hydrogel is 1-4%, depending on the NO level being delivered. The mediator is a derivative of benzophenone (sunscreen) and is used at 100 ppm in the wet hydrogel.

The generation of NO from the Bandage has been quantified in vitro using a gel (gelatin) containing a colorimetric sensor, 1,2-diaminoanthroquinone, (DAQ) which selectively reacts with NO to form a colorless product. The flux of NO (moles per minute) was calculated by following the loss of the DAQ from the gel. A formulation/device combination generating the appropriate NO flux to promote granulation tissue development (0.5-1.5 x 10^{-7} moles per minute = 50-150 nM per minute) during healing was identified and used in porcine wound healing studies [22].

Ischemic Wound Healing. Noxsano is collaborating with [name] (Ohio State University Laboratory Animal Resource, ULAR). [name] has extensive experience [23-27] in the development and application of wound models for the evaluation of wound healing technologies. Based on [name] advice, Noxsano undertook the Bandage evaluation using a porcine ischemic wound model, a good model for wound healing in chronic wounds [31]. The ischemic wound model involves creating a 12.5 cm x 5.0 cm flap with reduced blood flow (ischemia). In the center of the flap an 8 mm full thickness wound is created, and this wound is used to evaluate ischemic wound healing. The first ischemic wound study sought to validate our hypothesis that restoring approximately 1 x 10^{-7} moles per minute of NO delivered to an ischemic wound would promote granulation and therefore speed healing time.

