- The dressing is powered by a 3V battery commonly found in a wide range of consumer electronics. It presents no risk for electric field exposure, electrical shock, or electrocution.
- ♦ The dressing contains a safe, stable precursor to NO, sodium nitrite. Sodium nitrite is commonly used to tenderize and cure meats, and can safely be consumed.
- ♦ The mediator is a benzophenone derivative present at very low levels (100 ppm), and is similar in structure to a common sunscreen ingredient. It has no known adverse toxicological effects.
- ♦ The hydrogel is a medical grade supersorber, essentially the same material used in baby diapers. It has no known adverse toxicological effects.
- ♦ The hydrogel formulation does not directly contact the patient's skin. The formulation is contained in a medical grade nonwoven dressing material.

The factors described above lead Noxsano to the view that the proposed study device is 'non-significant risk' (NSR) as defined by the FDA in 21 CFR 812.3(m). In addition, the protocol has been designed to ensure that the subjects' health and safety is not imperiled.

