2.0 STUDY OBJECTIVES AND ENDPOINTS

2.1 Primary Objective

Group 1 (Safety): Healthy Volunteers. The initial phase of the study is designed to determine the safety of the study device in healthy volunteers without wounds. If there are no issues with tolerance, side effects, or adverse reactions in healthy volunteers, the second phase of the study will proceed with active wound care subjects.

For the purposes of this study, if two subjects experience an unacceptable adverse reaction warranting discontinuation of treatment in the opinion of the Investigators during the initial phase of the study, the study will be halted and the second phase (and the remainder of the initial phase, if applicable) will not be completed. Allergic reactions and infections at the bandage site will be considered unacceptable at any clinical severity; other adverse reactions will be deemed "unacceptable" by the Investigators on a case-by-case basis dependent upon clinical severity (App. A).

Group 2 (Efficacy): Wound Care Subjects. The second phase of the study is designed to determine the effectiveness of the study device in wound healing in subjects with active wounds (see Primary & Secondary Endpoints below).

[figure not shown]

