Therefore, Group 1 healthy volunteers are more likely to experience adverse events related to hypersensitivity and skin reactions, and are thus being limited to 3 days (up to 72) hours of Bandage wear. It is anticipated that symptoms will manifest within 24-72 hours of application and resolve within 7-10 days of removal, but could take as long as 30 days or more depending on individual skin regeneration. Regarding Group 2 wound care subjects, we expect manifestation and resolution of symptoms on the same timeline, but cannot state decisively as this is the first study in this population. Finally, as itching is a normal consequence of wound healing, we expect this to occur in the majority of Group 2 subjects. No preclinical evidence of significant risk has been demonstrated with the Noxsano Bandage, and therefore is not anticipated or expected during this study.

IRB# 1331496 Page 34 Version 6.0

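### Section 4.5 excludes known allergy to adhesives only, so a person with a known allergy to another listed component of the device is eligible as written

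*Combined protocol and SAP*

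**What the plan says.** Section 4.5 has one hypersensitivity exclusion per group. Group 1, criterion 3, reads "Subject has a known hypersensitivity to adhesives"; Group 2, criterion 9, reads "Subject with a known hypersensitivity to adhesives". Section 4.3 makes eligibility depend on the criteria in 4.4 and 4.5.

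Section 1.3.1 gives the hydrogel as "Medical grade cross-linked poly-(acrylic acid), sodium nitrite, buffer (pH 7.5-8.0), and an electrochemical mediator". Of the mediator it says: "The mediator is a derivative of benzophenone (sunscreen) and is used at 100 ppm in the wet hydrogel". Section 1.3.4 calls the mediator "similar in structure to a common sunscreen ingredient" and also states: "The hydrogel formulation does not directly contact the patient's skin".

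On consequences, section 2.1 says "Allergic reactions and infections at the bandage site will be considered unacceptable at any clinical severity". Two unacceptable reactions during the healthy-volunteer phase halt the study (sections 2.1, 3.3 and 5.7). Section 5.11 takes any subject in either group who has an allergic reaction at the application site off study treatment.

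**The concern.** By excluding adhesive allergy, the plan accepts that a known contact sensitivity is a reason not to enrol someone. It then stops at adhesives and gives no reason for leaving out the other materials it lists. This is the first clinical study of the device (section 1.3.2), and section 1.3.5 says the pig work could not show whether irritation occurs. Apart from the founders' own wear of up to 72 hours, the protocol reports no human tolerance experience.

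Two things are at stake. The first is an avoidable risk to a subject who has already declared the allergy. The second is what the trial learns. A reaction in someone known beforehand to be allergic says little about tolerability in other people, yet in Group 1 it counts in full towards halting the study. In Group 2 it costs a subject from a very small efficacy group.

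**Working it through.** The plan gives no error rate or operating characteristic for the halt rule and no rate of allergic reactions, so there is no figure to reproduce. The check compares the component list with the criteria and then counts consequences.

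**1. Components against criteria.**

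| Material | Where listed | Covered by a criterion in 4.4 or 4.5? |
|---|---|---|
| Adhesive | 4.5 | Yes, both groups |
| Benzophenone-derivative mediator, 100 ppm | 1.3.1, 1.3.4 | No |
| Sodium nitrite | 1.3.1, 1.3.4 | No |
| Cross-linked poly-(acrylic acid) | 1.3.1 | No |

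No criterion refers to device components in general. The connectors are conductive tape, which could fall under adhesives, so they are left out of the list of gaps.

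**2. Does anything else act as an exclusion?** Section 5.1 schedules a medical history at the Group 1 phone screen and at Group 2 screening/baseline. Section 5.11 lets the investigators withdraw a subject to protect health or safety. Both give an opportunity to notice a declared allergy, but neither makes it a ground for exclusion.

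**3. Consequence in Group 1.** The halt comes at 2 subjects. The trigger is worded as a reaction that, in the investigators' opinion, warrants discontinuation. Because allergic reactions are unacceptable at any severity and section 5.11 takes such subjects off treatment, one would count. Share of the trigger used: 1 / 2 = 50%. One more unacceptable reaction among the other 10 − 1 = 9 volunteers would halt the study.

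**4. Consequence in Group 2.** The two-subject rule covers only the initial phase, so it does not apply here. The stated consequence is removal from treatment: 1 / 10 = 10% of the efficacy group. Replacement is provided for only when a person does not attend for the first application (sections 4.3 and 5.11). Nothing provides for replacing a subject removed for an allergic reaction.

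**5. Likelihood.** Two quantities are needed: how common a known component allergy is among people screened, and how often such a person would react to the bandage. The documents give neither.

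**The case against.** The strongest case on the other side is that a reaction may be unlikely. The mediator is at 100 ppm, and section 1.3.4 says that neither it nor the hydrogel has known adverse toxicological effects, that sodium nitrite can be eaten safely, and that the formulation is enclosed in a nonwoven material away from the skin. Structural likeness to a sunscreen ingredient does not show that a sunscreen-allergic person would react. This stands, and it limits the size of the point. It does not close the gap. The dressing is soaked in 25-50 ml of water (section 6.3) and, in Group 2, goes over a wound for up to 3 months. The documents do not say that the nonwoven holds back dissolved components, though they do not report leaching either. A general toxicology statement also does not address a person who is already sensitised.

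Two stronger readings are tempting, and the documents support neither.

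- A reader might infer that the protocol itself predicts such allergies, because section 7.1.1 says "Group 1 healthy volunteers are more likely to experience adverse events related to hypersensitivity and skin reactions". That sentence is a conclusion from the preceding argument, also made in section 1.3.5, that the bandage raises nitric oxide above normal in healthy skin. The expected reactions are attributed to excess nitric oxide, and screening for component allergy would not reduce them.
- A reader might infer a large effect on the halt rule. At an assumed 5% reaction rate, the chance of 2 or more reactions in 10 is 1 − 0.599 − 0.315 = 8.6%. Once one volunteer has reacted, the chance of at least one more among 9 is 1 − 0.95^9 = 37%. But 37% is conditional on a first reaction, and a first reaction from any cause gives the same jump, so the contrast does not measure the missing criterion. An unconditional figure needs the two unknown quantities. As illustration only, suppose 1% of volunteers have a known component allergy and the other 99% react at 5%. If all allergic volunteers react, the per-subject rate is 0.99 × 0.05 + 0.01 = 0.0595 and the halt probability is 11.6%. If half react, the rate is 0.0545 and the halt probability is 10.0%. Every input here is assumed.

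**Conclusion.** The point holds as a gap in the eligibility criteria. As written, a person with a known allergy to the mediator, nitrite or polyacrylate is not excluded from either group. If that person is enrolled and reacts, the cost is one of the two reactions that halt the study (Group 1), or one of 10 subjects taken off treatment without provision for replacement (Group 2).

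How often this would happen cannot be stated from the documents, and it may be seldom. There is no internal contradiction and no demonstrated material effect on the halt rule or the primary endpoint. This is a worthwhile, low-cost improvement.

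The conclusion rests on the criteria as listed in 4.4 and 4.5. The questionnaire, consent forms and bandage information sheet (Appendices A, D, E and G) and the section 10.0 addendum on two device-related adverse events were not available to check. They might ask or warn about allergy, but section 4.3 ties eligibility to the listed criteria.

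**What to change.** In section 4.5, reword Group 1 criterion 3 and Group 2 criterion 9 to *known hypersensitivity to adhesives or to any component of the study device*. Give screeners the component list in plain language: the benzophenone-type mediator (with sunscreen as the everyday example), nitrite and acrylic polymer. Add the question to the Group 1 phone screen and to the Group 2 medical history.

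The cost is one line in each exclusion list, one extra screening question and possibly a few more screen failures; the documents give no figure for how many. If Group 1 is already complete, the Group 2 change is still worth making, because exposure there is longer and over broken skin.

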3.2 Subject Population and Sites

Group 1: Initial subjects will be limited to healthy volunteers with intact skin on their lower extremities. Five (5) white subjects and 5 black or African American subjects will be enrolled to evaluate skin differences. Group 1 (healthy volunteers without wounds) will have all follow-up completed and the results assessed before the investigators initiate prior to proceeding to Group 2 (wound care subjects).

Group 2: The subsequent wound care subject study will include 10 subjects from the patient population treated at the OhioHealth Riverside Methodist Hospital Critical Limb Care Center for lower extremity ulceration attributed to diabetes and/or arterial insufficiency.

[figure not shown]

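### Group 1, the ten-person safety gate, lacks the exclusion for current enrolment in another interventional study that Group 2 has, so another study's product could add to or mask bandage reactions

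*Combined protocol and SAP*

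**What the plan says.** Section 4.5 lists the exclusions by group. The last Group 2 item, number 14, is "Subject is currently enrolled in another interventional study". The Group 1 list has seven items and ends with "Subject is unable to give informed consent". None of the seven, and none of the five Group 1 inclusions in section 4.4, mentions another study or an investigational product.

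The nearest Group 1 safeguard is exclusion 4: "Subject is on any prescription medications, including contraceptives". It applies at entry. The same item adds that "subjects who initiate prescription medications during study participation will continue in the study", because the device is worn for only three days.

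Group 1 volunteers come from hospital flyers and from ResearchMatch (section 4.1.2), which section 4.1.1 says "consists of a registry of volunteers that have signed up to receive notifications about potential research studies". On size, section 3.2 states: "Five (5) white subjects and 5 black or African American subjects will be enrolled to evaluate skin differences". There is no control group, and section 3.2 requires Group 1 follow-up to be complete and assessed before Group 2 starts.

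The halting rule in section 2.1, repeated in 3.3 and 5.7, applies "if two subjects experience an unacceptable adverse reaction warranting discontinuation of treatment in the opinion of the Investigators" during the first phase. Allergic reactions and infections at the device site count at any severity; other reactions are judged case by case.

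**The concern.** The plan treats enrolment in another interventional study as a reason to keep a patient out of Group 2, but does not ask the question in Group 1 and gives no reason for the difference. Yet Group 1 is where a single person's reaction carries most weight: ten volunteers, no comparator, and a threshold of two that decides whether the second phase happens.

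A concurrent study product could distort that count in two ways. It could cause a reaction that is counted towards the threshold. Section 7.1.1 classes systemic effects such as fever, nausea, vomiting and hypotension as adverse reactions, and the halting rule does not explicitly require that a reaction be related to the device. Or the product could suppress a genuine bandage reaction, for example if it is anti-inflammatory or anti-allergic, so that the device looks better tolerated than it is.

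**Working it through.** **Step 1. Do other Group 1 provisions cover the gap?**

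- Exclusion 4 (section 4.5) concerns prescription medications at entry. An investigational drug, vaccine, topical product or device is not plainly a prescription medication.
- The concomitant-medication list (section 5.2) covers prescription, over-the-counter and topical products at each visit. It does not name investigational products or devices, and listing a product does not exclude the volunteer.
- Relatedness to device and procedure is recorded for each adverse event (sections 7.2 and 7.2.2). The halting rule does not refer to that grading.
- The telephone pre-screen (section 4.1.1) covers medical history and eligibility. Enrolment in another study is not a Group 1 eligibility item.

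Each is a partial safeguard. None asks the question that Group 2 exclusion 14 asks.

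**Step 2. Inputs for an illustration.** From the documents: n = 10 volunteers and a halt at 2 reactions. The plan states no operating characteristics for this rule, so there is no figure to reproduce. Assumed: the bandage's unacceptable-reaction rate p, the other product's rate q, and the number co-enrolled k. Reactions are taken as independent, and every outside reaction as counted, which ignores investigator judgement and so gives an upper estimate.

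**Step 3. No co-enrolment.** P(halt) = 1 − (1−p)^10 − 10p(1−p)^9. At p = 5%: 1 − 0.5987 − 10 × 0.05 × 0.6302 = 0.0861.

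**Step 4. Outside reactions added.** A co-enrolled volunteer reacts with probability r = 1 − (1−p)(1−q). With k = 1:

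P(halt) = 1 − (1−r)(1−p)^9 − [r(1−p)^9 + (1−r) × 9p(1−p)^8].

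- p = 5%, q = 10%: r = 0.145, so 1 − 0.5389 − (0.0914 + 0.2553) = 0.1145 after carrying full precision (0.1144996, or 11.4%).
- p = 5%, q = 20%: r = 0.24, so 1 − 0.4790 − (0.1513 + 0.2269) = 0.1429 after carrying full precision.

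The same calculation over a range of assumptions:

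| Bandage rate p | k = 0 | k = 1, q = 10% | k = 1, q = 20% | k = 2, q = 10% | k = 2, q = 20% |
|---|---|---|---|---|---|
| 0% | 0% | 0% | 0% | 1.0% | 4.0% |
| 2% | 1.6% | 3.1% | 4.6% | 5.3% | 10.4% |
| 5% | 8.6% | 11.4% | 14.3% | 14.6% | 21.3% |
| 10% | 26.4% | 29.9% | 33.4% | 33.4% | 40.5% |

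**Step 5. Bandage reactions masked.** If reactions are fully suppressed in k volunteers, only 10 − k can contribute: P(halt) = 1 − (1−p)^(10−k) − (10−k)p(1−p)^(9−k). At p = 20%:

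- k = 0: 1 − 0.1074 − 0.2684 = 0.6242
- k = 1: 1 − 0.1342 − 0.3020 = 0.5638
- k = 2: 1 − 0.1678 − 0.3355 = 0.4967

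| Bandage rate p | k = 0 | k = 1 | k = 2 |
|---|---|---|---|
| 10% | 26.4% | 22.5% | 18.7% |
| 20% | 62.4% | 56.4% | 49.7% |
| 30% | 85.1% | 80.4% | 74.5% |

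**The case against.** The difference between the groups may be deliberate. Group 2 is treated for up to three months with a healing endpoint that another intervention could confound directly; Group 1 wears one device for up to 72 hours, and the protocol already tolerates medication started during the study on the ground of that short period. This explains why the criterion matters for Group 2, but not why Group 1 can do without it: tolerating new medication after entry is not the same as admitting someone already exposed to an unknown product.

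A reader might infer that a reaction to another product could never be told apart from a bandage reaction. The documents do not support that. Exposure is confined to a shaved 4 x 4 cm area of the left calf (sections 5.6 and 5.7), photographed before application, at removal and at each follow-up visit (section 5.3). Relatedness is graded, the any-severity trigger is tied to the device site, and everything else goes through the investigators. These provisions are a real defence against miscounting. They help much less with masking, because a reaction that does not appear cannot be photographed or graded.

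A reader might also infer that registry recruitment means volunteers are in other trials. Section 4.1.1 describes people who signed up for notifications, and the registry is one of two sources. Overlap is plausible, not shown.

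Finally, one could quote the much higher halt probability that applies once an outside reaction has been counted. That assumes co-enrolment, a reaction and its miscounting have all occurred, so it does not measure the effect of the missing criterion.

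Two limits remain. The pre-screen questions, recruitment notices and consent forms are not in the text available for review and might ask about other studies. That text also does not establish whether Group 1 is still enrolling.

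**Conclusion.** The gap stands as a minor one. Group 2 has the exclusion, Group 1 does not, and no other Group 1 provision in the reviewed text clearly replaces it. Because the threshold is two among ten, even one co-enrolled volunteer can shift the halt probability: by 2.8 or 5.7 percentage points upward at p = 5% (q = 10% or 20%), and by 6.0 points downward with full masking at p = 20%. All these rates are assumptions, and the upward figures ignore the investigators' filter. If the bandage caused no unacceptable reactions, other products could trigger a halt only with at least two co-enrolled volunteers.

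This does not show that the Group 1 result is unreliable, or that co-enrolment occurred. It shows a confounder that the plan guards against in one group and leaves unaddressed in the other. The absence of an explicit relatedness condition in the halting rule is a related but separate matter.

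**What to change.** Add the wording of Group 2 exclusion 14 to the Group 1 exclusions in section 4.5, and put the question to volunteers at the telephone pre-screen described in section 4.1.1. The cost is one criterion, one question and a slightly smaller volunteer pool; sample size, visits and analysis do not change. If Group 1 enrolment has already closed, establish whether any of the volunteers was in another interventional study during participation, and report the answer with the Group 1 safety result.
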